This visit is scheduled after a pre-visit phone call or at the time of the dating ultrasound visit. Pre-operative examination and operative consents will be reviewed and signed per usual practice. Research staff will review the study and obtain informed consent for the study. Office or formal radiologic ultrasounds will be performed based on clinical indication. Study medication will then be dispensed with instructions to take 18-24 hours prior to scheduled pre-operative visit. All women will receive a diary to collect side effect information.

Day 2: Pre-operative visit

Women will return for their scheduled pre-operative visit the day prior to their scheduled procedure. Diaries will be collected and reviewed and osmotic dilators (Dilapan-S 4-mm) will be placed. Pain score measured by VAS will be collected at time of dilator placement.

Day 3: Standard dilation and evacuation procedure

Participants will proceed to the operating room and undergo sedation per anesthesia guidelines. Initial cervical dilation using Pratt dilators will be measured after dilator removal. Standard dilation and evacuation will be performed.

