1.1.10 Data analysis

As the primary outcome is a dichotomous variable, I will perform logistic regression analyses. The number of cervical dilators will be collected either at time of clinic visit or by chart review. Missing data will be minimized by allowing for exclusion of any potential participant who may be judged to have increased risk for loss to follow up at time of enrollment and prior to randomization. We will include all women randomized and perform intent-to-treat analysis with no apparent exclusions. In addition, a second analysis will be conducted excluding women who do not report ingesting the study medication.

At time of enrollment, we plan to collect baseline demographic data, including age, race, ethnicity, education level, obstetric history, and history of cervical procedures. I will perform univariate analyses to compare the two study groups at baseline. If any variables are significantly different, I will utilize those variables to adjust the logistic regression for the primary outcome. While not powered to detect a statistically significant difference among the two groups for the secondary outcomes, exploratory analyses will be performed to identify possible trends and areas of interest for a subsequent larger trial. The data analysis will be as follows:

Secondary outcome	Data analysis plan
Proportion of appropriate number of dilators	Logistic regression
Cervical dilation at time of procedure	Linear regression
Number of tablets of ibuprofen and Tylenol #3 utilized with dilators in place	Logistic regression
Proportion of women requiring mechanical dilation at time of procedure	Logistic regression
Pain at time of dilator placement (VAS)	Linear regression
Provider perception of overall ease of procedure	Logistic regression
Provider perception of difficulty in dilating the cervix when required	
Overall complication and adverse event rate	Logistic regression

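### The exploratory analgesic tablet count is assigned logistic regression with no ordinal form or cut-point stated. An ordinal model on one pre-stated count would keep the information that a binary split discards.

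*Combined protocol and SAP*

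**What the plan says.** All of the following is in the combined protocol and SAP.

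- **Outcome and method.** One row of the secondary outcome table in 1.1.10 is "Number of tablets of ibuprofen and Tylenol #3 utilized with dilators in place", with logistic regression as its analysis. No cut-point, categories or ordinal model is given. Nor does the row say whether the two drugs are counted together or apart.
- **What logistic regression means here.** The opening of 1.1.10 gives the dichotomous nature of the primary outcome as the reason for logistic regression. The other two numeric rows of the table, cervical dilation and the pain VAS, are assigned linear regression.
- **Status.** Section 1.1.10 states: "While not powered to detect a statistically significant difference among the two groups for the secondary outcomes, exploratory analyses will be performed". The purpose is to point to trends for a later, larger trial.
- **Data source.** Under 1.1.5, Day 1: "All women will receive a diary to collect side effect information". Under Day 2, the day before the procedure: "Diaries will be collected and reviewed and osmotic dilators (Dilapan-S 4-mm) will be placed". The dilators come out on Day 3. Section 1.1.9 refers to paper data collection forms without listing their contents.

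**The concern.** A number of tablets is not dichotomous. If the row means binary logistic regression, as the section's own justification suggests, the analyst must first reduce the count to two classes. Any use versus none, above versus below the median, and some other threshold are all consistent with the text. They are different outcomes that keep different amounts of information.

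The row matters a little more than its exploratory label suggests. The VAS is tied to placement ("Pain score measured by VAS will be collected at time of dilator placement"), so tablet use is the only listed outcome that bears on pain between placement and removal. If the table is to guide a larger trial, this row should use the count it names.

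At stake is the usefulness of one exploratory comparison. The trial's main conclusion does not depend on it.

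**Working it through.** **1. The plan's own figure.** There is none for tablets. The only sample size is for the primary outcome in 1.1.11: 10% vs 45%, 80% power, alpha 0.05.

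- Two-sided, uncorrected, with p̄ = 0.275: n = [1.96√(2 × 0.275 × 0.725) + 0.8416√(0.10 × 0.90 + 0.45 × 0.55)]² / 0.35² = (1.2377 + 0.4889)² / 0.1225 = 24.3 per arm.
- With continuity correction: (24.34/4) × [1 + √(1 + 4/(24.34 × 0.35))]² = 29.8, so 30 per arm and 60 in total, as stated.
- 60 × 1.10 = 66, as stated.

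None of this uses the tablet count.

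**2. Inputs for the tablet outcome.** The 33 per arm comes from 1.1.1. Everything else is assumed: a single negative binomial count with variance = mean + mean²/size, size 1, 2 or 5, four pairs of means, and two-sided 0.05. The proportional-odds likelihood-ratio test is compared with a Pearson test on the same data, cut above the pooled median or above zero (2,500 simulated trials per setting).

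| Size | Means | Proportional odds | Median split | Any use | Loss, median | Loss, any use |
|---|---|---|---|---|---|---|
| 1 | 1 vs 0.5 | 37% | 31% | 31% | 6 | 6 |
| 1 | 2 vs 1 | 48% | 40% | 31% | 8 | 17 |
| 1 | 4 vs 2.5 | 30% | 26% | 14% | 4 | 16 |
| 1 | 4 vs 2 | 55% | 46% | 24% | 9 | 31 |
| 2 | 1 vs 0.5 | 47% | 40% | 41% | 7 | 6 |
| 2 | 2 vs 1 | 66% | 55% | 40% | 11 | 26 |
| 2 | 4 vs 2.5 | 50% | 40% | 16% | 10 | 34 |
| 2 | 4 vs 2 | 79% | 68% | 32% | 11 | 47 |
| 5 | 1 vs 0.5 | 56% | 46% | 49% | 10 | 7 |
| 5 | 2 vs 1 | 80% | 69% | 50% | 11 | 30 |
| 5 | 4 vs 2.5 | 71% | 60% | 21% | 11 | 50 |
| 5 | 4 vs 2 | 95% | 87% | 43% | 8 | 52 |

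Before rounding, the losses are 4.5 to 11.6 points (median split) and 5.9 to 52.2 (any use). With no true difference the likelihood-ratio test rejects in 5.1 to 6.2%, slightly above nominal. A rank test is therefore a useful second reference: against it the losses are 4.2 to 11.0 and 4.3 to 52.3 points (10,000 runs).

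**3. Why any use can lose so much.** P(no tablets) = [size/(size + mean)]^size.

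- Size 5, means 4 vs 2: (5/9)^5 = 0.053 and (5/7)^5 = 0.186. Halving the mean moves any use only from 94.7% to 81.4%.
- Size 1, means 1 vs 0.5: 1/2 and 2/3. Any use is 50% vs 33%, and the split loses little.

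The cost therefore depends on how much analgesia women take, which the documents do not say.

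**4. One count or two.** If each tablet were equally likely to be either drug, a total with means 2 vs 1 would split into two counts with means 1 vs 0.5 and the same size. From the table, for sizes 1, 2 and 5:

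- proportional odds on the total: 48%, 66%, 80%
- proportional odds on one drug: 37%, 47%, 56%
- median split of the total: 40%, 55%, 69%

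A separate test per drug is thus weaker than a median split of the total. Calling a result positive if either drug is significant rejects in about 9% under no difference.

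**The case against.** - **Logistic regression can mean ordinal logistic regression.** If that was intended, only one word is missing. This stands, and it makes the change nearly free. But the section links the method to a dichotomous outcome, so an analyst following the text would more naturally fit a binary model.
- **The outcome is exploratory.** Power is not a design target here: "exploratory analyses will be performed to identify possible trends and areas of interest for a subsequent larger trial". This also stands and caps the weight of the point. It is not a reason to discard information already collected.
- **The size is entirely assumed.** True. The ranges are wide, and at low tablet use the any-use split costs only about 4 to 7 points. The direction is the same in all twelve settings.
- **Post hoc cut-points.** A reader might infer that the threshold will be picked after the data are seen. Under no difference, taking the best of four thresholds (above 0, 1, 2 or 3) would reject in 15 to 17%. No passage proposes this. The text only leaves the threshold open, so that figure is not a property of the plan.
- **The diary.** A reader might infer that the outcome cannot be collected, because the diary is handed in when the dilators are placed. The documents do not support that. The diary is assigned to side effects and is never said to record tablets, so its Day 2 collection contradicts nothing. The forms in 1.1.9 are not shown, and staff see the women on Day 3. What remains is that no source for the placement-to-removal window is described.

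**Conclusion.** The point holds as a modest improvement to one exploratory analysis. Section 1.1.10 gives a count a method that the section itself associates with two-class outcomes, and it names neither a cut-point nor an ordinal form. Under the assumed inputs (33 per arm, one negative binomial count), a median split costs roughly 4 to 12 power points and an any-use split roughly 4 to 52. These figures do not carry over to separate tests for ibuprofen and Tylenol #3. Nothing in the documents requires separate tests, and under an even split they would give back the gain.

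The missing data source is a request for clarification only. It is not evidence that tablet use goes unrecorded. The row "Provider perception of overall ease of procedure" also has no stated coding, but its scale is not described, so no loss can be argued there. The primary analysis and the 66 women are untouched.

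**What to change.** **In 1.1.10**, change the analysis cell for this row to: *Proportional-odds (ordinal) logistic regression on the number of tablets*. Add that one form of the count, for example the combined total of both drugs, is the stated form for this comparison, and that per-drug counts are reported descriptively. The investigators should choose the form. The statistical requirement is only that a single form is fixed before the data are seen.

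**In 1.1.5 or 1.1.9**, as a clarification, name the form that records tablets taken between dilator placement on Day 2 and removal on Day 3. If none does, one item at the existing Day 3 visit would cover it. Such an item relies on overnight recall. If 20% of women were off by one tablet, proportional odds would lose an assumed 0.5 to 8.4 power points.

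**Cost.** One table cell and one or two sentences, with no added participants or visits. The result becomes a common odds ratio, which is less direct to read than a difference in proportions, and 66 women allow only a weak check of the proportional-odds assumption. Both are acceptable for an exploratory outcome.

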1.1 Design methodology

1.1.1 *Research design and general methodological approach*

The planned research design is a double-blind, placebo-controlled randomized trial.

- A. Study arm: mifepristone 200 mg orally 18-24 hours prior to osmotic dilator placement
- B. Control arm: placebo oral medication 18-24 hours prior to osmotic dilator placement

The total number of women will be 66 and 33 women will be allocated to each group (Appendix – CONSORT Flow Diagram).

1.1.2 *Criteria for the selection of subjects*

Inclusion criteria:

- A. Women planning dilation and evacuation with cervical dilator placement at gestational ages 20 weeks 0 days to 23 weeks 6 days on procedure day
- B. English-speaking/writing

Exclusion criteria:

- A. Allergy to mifepristone
- B. Any condition that in the opinion of the investigator could impede study participation or collection of study data

1.1.3 *Subject recruitment and allocation*

Participant identification

Potential participants will be identified either at time of referral to UC Davis Family Planning Center from outside clinics after dating ultrasound is performed or when presenting directly for dating ultrasound at UC Davis Family Planning Center.

Pre-visit phone call

For women who have been referred to UC Davis and have already had a dating ultrasound, research staff will call to explain the study. For women not interested in the study, a standard pre-operative visit per clinic guidelines will be scheduled. For women who are

interested in enrolling in the study, a screening and enrollment visit will be scheduled.

Women will be notified that they will be randomly allocated to mifepristone or placebo medication.

1.1.4 *Description of the drugs and devices to be studied*

Mifepristone exerts anti-progestin activity by binding with high affinity to progesterone receptors and causing an increase in glycosaminoglycans, such as hyaluronic acid, increases collagenase activation and tissue water content ¹⁴⁻¹⁷. These actions promote softening and dilation of the cervix ^{14,15} and also increase the myometrial response to exogenous prostaglandins, such as misoprostol ¹⁷.

1.1.5 *Admission procedure*

Day 1: Screening and Enrollment

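### Dilation difficulty is rated only in women who needed dilation, a subset that treatment may change, so the comparison is not randomized and its bias has no known direction

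*Combined protocol and SAP*

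**What the plan says.** Section 1.1.10 lists the provider's rating as "Provider perception of difficulty in dilating the cervix when required". Another row of the same table is "Proportion of women requiring mechanical dilation at time of procedure", so the condition for having a rating is itself compared between arms. Section 1.1.4 says of mifepristone's effects: "These actions promote softening and dilation of the cervix". On the analysis population, section 1.1.10 says "We will include all women randomized and perform intent-to-treat analysis with no apparent exclusions". On the status of these outcomes it says "While not powered to detect a statistically significant difference among the two groups for the secondary outcomes, exploratory analyses will be performed"; the stated purpose is to find trends worth pursuing in a larger trial.

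No rule is given for women who need no dilation. No expected rate is given for need or for difficulty, and no rating scale is shown. The method cell for this row is blank in the text available. That may be an extraction loss, and nothing here depends on it.

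**The concern.** Randomization makes the two groups of 33 comparable. It does not make comparable the women in each group who go on to need dilation. If mifepristone changes who needs it, the rated women in the two arms are different kinds of patient. A difference in their ratings then mixes the drug's effect on difficulty with the drug's effect on who is rated.

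The natural picture is that the drug spares the women whose cervices were nearly open already. The rated mifepristone women are then the harder cases, set against a broader mix on placebo. An effective drug could look neutral or even harmful on this row. Because these outcomes are meant to guide a later trial, a row that cannot be interpreted is a defect even without a formal claim resting on it.

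**Working it through.** **The plan's own figure.** None is stated for this outcome. The only sample-size figure is for the primary outcome (section 1.1.11: 10% against 45%, 80% power, alpha 0.05, total 60). With a two-sided test, the uncorrected size per arm is

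n = [1.960·√(2·0.275·0.725) + 0.842·√(0.10·0.90 + 0.45·0.55)]² / 0.35² = 24.3.

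The continuity correction gives (24.3/4)·[1 + √(1 + 4/(24.3·0.35))]² = 29.8, so 30 per arm and 60 in total. Then 60 × 1.10 = 66. The figure reproduces, and the present point does not touch it.

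**Illustration 1: uniform shift.** These inputs are assumed, not taken from the documents. Latent difficulty is normal with SD 1, dilation is needed above a common threshold, and treatment lowers everyone by the same amount. Need is 50% on placebo and 25% on mifepristone.

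- Threshold on placebo: 0. For 25% to exceed 0 after the shift, the shift is -0.674.
- Mean among placebo women needing dilation: φ(0)/0.50 = 0.399/0.50 = 0.798.
- Mean among mifepristone women needing dilation: -0.674 + φ(0.674)/0.25 = -0.674 + 1.271 = 0.597.
- Subset difference: 0.597 - 0.798 = -0.20, against a true -0.67. That is 0.201/0.674 = 30%.
- Check: women who would need dilation in either arm average 1.271 on placebo and 0.597 on mifepristone, a difference of -0.674. The lost 70% is therefore selection.
- Numbers rated: 33 × 0.50 ≈ 16 and 33 × 0.25 ≈ 8.

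With need of 30-70% on placebo and 15-50% on mifepristone (lower on mifepristone), the subset keeps 23% (30% against 15%) to 43% (70% against 50%) of the shift.

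**Illustration 2: varying who is spared.** The range above varies rates inside one model. The next table varies the model. Difficulty is a yes/no rating, 40% of placebo dilations are called difficult, and each scenario uses 1,000,000 simulated women. Entries are risk differences, mifepristone minus placebo.

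| Assumed pattern | Among women needing dilation | Effect on difficulty built in |
|---|---|---|
| Resistance falls 0.25-1.0 SD in everyone; placebo need 40-80% | -0.04 to -0.20 | -0.10 to -0.57 in women needing dilation under either arm |
| Only easier cases are spared; difficulty unchanged | +0.12 to +0.28 | none |
| Need removed at random, 60% to 30% | 0.00 | none |
| Mainly the hardest cases spared, 60% to 34% | -0.14 | none |

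The rows run from attenuation through false harm and no bias to false benefit. In the first row the subset would hold about 13-26 placebo and 3-24 mifepristone women.

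**What scoring everyone adds.** This uses 33 per arm, two-sided 5% tests, and an assumed six-level score with zero for no dilation, compared by Mann-Whitney. Power for need alone is an uncorrected chi-square by exact enumeration.

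| Need, placebo / mifepristone | Subset ratings | All women scored | Need for dilation alone |
|---|---|---|---|
| 50% / 25% | 10-11% | 59-61% | 59% |
| 70% / 40% | 23-24% | 80% | 74% |

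The two-figure entries are separate runs of 4,000 simulated trials. Most of the gain in the third column is already available from the need-for-dilation row, so it is not a gain in power on difficulty itself.

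**The case against.** A reader might infer that the comparison is bound to hide a benefit. The documents do not support that. They do not say which women are spared dilation and give no need rates, and the second illustration shows zero or reversed bias under other patterns. Only the weaker statement stands: attenuation or apparent harm is the most plausible direction, on the assumption that easier cases drop out.

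A reader might also infer that a later trial would be misled. The same table analyses need for dilation, cervical dilation at the procedure, and "Provider perception of overall ease of procedure", none restricted to women who needed dilation. In the first illustration the drug's effect would show in the need row. If measured cervical dilation shifted by the same 0.67 SD, a comparison of 33 per arm would have about 77% power. This lowers the stakes considerably, but it does not make the conditional row interpretable.

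Exploratory status is the strongest reply on severity, and it stands as far as that goes. Lack of power explains imprecision, not selection. Likewise, "The planned research design is a double-blind, placebo-controlled randomized trial" protects the rating from knowledge of allocation but does not restore comparability of the women rated.

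Finally, an all-women score answers a different question, need and difficulty together. That is a true limitation, and the score should be presented as such.

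**Conclusion.** The point holds as a structural defect in one secondary outcome. The comparison conditions on a post-randomization event that treatment is expected to change, it departs from the plan's intent-to-treat statement, and no other provision repairs it. The size is unknown because the documents give no rates. The loss of about 70% of a 0.67 SD shift rests on the assumed normal model with a common threshold and 50% against 25% need. The direction is not established.

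Severity is minor. The outcome is declared exploratory and unpowered, related unrestricted outcomes sit beside it, and the primary analysis and the 66-woman sample size are untouched.

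**What to change.** In section 1.1.10, define this outcome for all randomized women who have the procedure, on an ordered scale: dilation not required as the lowest category, then the difficulty ratings in order. Compare arms as randomized, by proportional-odds logistic regression or a Wilcoxon test, and keep the exploratory label. Report the ratings among women who needed dilation descriptively only, beside the number needing dilation in each arm.

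State that the score combines need with difficulty, overlaps the need-for-dilation outcome, and is to be read with it. Any gain in power should not be presented as evidence about difficulty alone.

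The cost is analysis wording plus a definition of the rating categories, since the documents show no scale. Both components are already planned outcomes, so no new measurement and no change in sample size should be needed.

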1.1.11 Number of subjects and statistical power

	Control group
--	---------------

% with +2 dilators	1	5	10	15	20
Study group	10	242	950	--	--
	20	100	176	438	1864
	30	60	86	144	268
	35	50	68	102	166
	40	42	54	76	114
	45	36	44	60	84
	50	30	38	50	66
	60	24	28	34	44
	70	18	22	26	30
	80	14	16	20	22

The appropriate number of dilators is based on gestational age at this university:

- a. 20 weeks 0 days to 20 weeks 6 days: at least 5 dilators
- b. 21 weeks 0 days to 21 weeks 6 days: at least 6 dilators
- c. 22 weeks 0 days to 23 weeks 6 days: at least 7 dilators

Without adjunctive medications, it is assumed that placing two more than the standard number of dilators will be difficult and a rare occurrence in about 10% of women. With adjunctive preparation with mifepristone, dilator placement will lead to an increased proportion of women (45%) receiving two additional dilators than the indicated number. We require 60 participants to detect a difference of 35% between the two groups and maintain 80% power and an alpha of 0.05. To account for medication nonadherence, we plan to recruit 10% more patients for a total of 66 women.
